10.6 Reporting Procedures for Related Unexpected Serious Adverse Events

A serious adverse event (SAE) occurring to a participant should be reported to the REC that gave a favourable opinion of the study where in the opinion of the Medical Reviewer the event was 'related' (resulted from administration of any of the research procedures) and 'unexpected' in relation to those procedures. Reports of related and unexpected SAEs should be submitted within 15 working days of the Chief Investigator becoming aware of the event, using the HRA report of serious adverse event form (see HRA website).

11. STATISTICS AND ANALYSIS

11.1. Statistical Analysis Plan (SAP)

The plans for the statistical analysis of the trial are outlined below. A separate SAP document will be produced prior to study analysis.

11.2. Description of Statistical Methods

The primary outcome measure will be analysed using a mixed effect model with the mean of the overnight (12 midnight to 7am) glucose levels from Days 5, 6, and 7 from both treatment arms as the dependent variable. Treatment allocation will be included as a binary factor with adjustments for age, sex, diabetes status (confirmed or prediabetic), BMI and other important factors.

Secondary outcomes will also be assessed using mixed effect models as described above. A separate secondary analysis of 24 hour glucose profiles will be analysed by comparing the area under the curve analysis.

11.3. Sample Size Determination

The sample size calculation is based on the difference in mean overnight glucose levels. This was chosen as the primary outcome as paired pilot data exists for this outcome, unlike other CGM metrics like MAGE or NMAGE which are instead included as secondary outcomes. The sample size calculation is based on pilot data from Chopra *et al.* (74), who looked at the difference in overnight blood glucose levels measured in a hospital setting over three nights of CPAP withdrawal in patients with T2DM and OSA. They found a between group difference of 17.2 19.0 mg/dl. Based on this, in order not to miss a between-group difference in overnight glucose levels of 17.2mg/dl between CPAP withdrawal and continued CPAP with a two-sided alpha of 0.05 and a beta of 0.8 would require 22 participants in a crossover study. An alternative would be to base our power calculation on data from Mokhlesi *et al.* (76), who looked at the difference in 24 hour blood glucose levels measured in hospital over 7 days in patients treated with CPAP with T2DM

and OSA. They found a 13.5 13.5 mg/dl improvement in 24 blood glucose levels with CPAP therapy. Based on this, in order not to miss a between group difference in 24-hour glucose levels of 13.5 mg/dl between CPAP withdrawal and continued CPAP with a two-sided alpha of 0.05 and a beta of 0.8 would require 18 participants in a crossover study.

Taking the more conservative estimate of 22 participants, and allowing for only 87% of CGM monitoring sensors surviving the 10 day follow-up period (53) from application, gives 25 patients. In previous parallel CPAP withdrawal trials drop-out rates following randomisation has been 1% (65). Therefore, allowing for a more conservative drop-out rate of 10% we will aim to randomise 30 patients. However, when 22 patients have completed the trial per protocol with sufficient CGM data recruitment will be stopped.

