Others have used similar short-term CPAP withdrawal protocols to demonstrate changes in glycaemic control both in patients without diabetes, and patients with T2DM not on insulin (74). They conducted randomised cross-over trial of three nights CPAP withdrawal versus continued CPAP. They conducted a full in-lab polysomnography (PSG) on the 3rd night of CPAP withdrawal and compared this to an on CPAP PSG night. They looked at blood glucose levels drawn from a venous catheter at regular intervals throughout the night. They found that CPAP withdrawal increased overnight glucose levels by 5.57 mg/dl (95% confidence interval or CI 0.59, 10.55, p=0.028). In a subgroup analysis they showed that this effect was only in the diabetic patients, with CPAP withdrawal increasing blood glucose levels by 17.2mg/dl in diabetic participants (95% CI 0.13, 34.6, p=0.04). It is worth noting that this was not a pre-planned subgroup analysis and that only 7 of 31 patients were diabetic. Other hospital based studies have explored the effect of CPAP on blood glucose control, with one randomised control trial enrolling patients with OSA and "prediabetes" and admitting them to hospital for two-weeks (75). Patients were randomised to either 8 hours per night of CPAP or oral placebo on a 2:1 basis and had attended PSG every night with CPAP adherence ensured by continual supervision. They then assessed the glucose response curve following an oral glucose tolerance test (OGTT) in the morning. They showed small improvements in the glucose response curve and in insulin sensitivity.

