8.2. Inclusion Criteria

- Participant is willing and able to give informed consent for participation in the trial.
- Male or Female, aged 18 years or above.
- Objectively confirmed obstructive sleep apnoea (at the time of original diagnosis) with an oxygen
 desaturation index (ODI ≥4% dips) of >20/h or/and an apnoea/hypopnoea index of >20/hour (this
 threshold will exclude subjects with borderline OSA, in whom there may be little treatment effect).
- Type 2 diabetes mellitus or HbA1c ≥6.0% (42mmol/l) at screening visit.
- In the Investigator's opinion, is able and willing to comply with all trial requirements.
- Willing to allow his or her General Practitioner and consultant, if appropriate, to be notified of participation in the trial.
- Currently >20/h oxygen desaturations (≥4% dips) returning on any night during a screening period
 of ambulatory nocturnal pulse oximetry performed during a 4-night period without CPAP.
- Treated with CPAP for more than 3 months, minimum compliance 6h per night, where available
 an AHI <10 with treatment (according to machine download data), and ODI < 10 confirmed on
 CPAP during screening oximetry.

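### The sample size rests on an effect seen in diabetic patients only, so the stated 80% power is not established for the mixed T2DM and prediabetes sample that is enrolled

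*Protocol*

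**What the plan says.** Section 11.3 takes its target difference and spread from a cited crossover study of CPAP withdrawal: "They found a between group difference of 17.2 19.0 mg/dl". The sign between the two numbers was lost in the text, and I read them as mean and SD. The section describes the source as "three nights of CPAP withdrawal in patients with T2DM and OSA" and concludes that "a two-sided alpha of 0.05 and a beta of 0.8 would require 22 participants in a crossover study". A second calculation, from a one-week CPAP treatment study in T2DM, uses 13.5 and 13.5 mg/dl and gives 18. The larger number is kept, and recruitment stops at 22 completers with sufficient glucose data.

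Section 5 describes the same withdrawal study more fully. Its whole-sample effect was 5.57 mg/dl (95% CI 0.59 to 10.55). In a subgroup analysis "this effect was only in the diabetic patients", at 17.2 mg/dl (95% CI 0.13 to 34.6). The protocol itself notes that this subgroup was not pre-planned and that "only 7 of 31 patients were diabetic".

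The trial admits "Type 2 diabetes mellitus or HbA1c ≥6.0% (42mmol/l) at screening visit" (section 8.2). No minimum or maximum share is set for either group, and randomisation is unstratified (section 9.4). The primary model in section 11.2 has a single treatment factor, with adjustment for age, sex, "diabetes status (confirmed or prediabetic), BMI and other important factors". Section 11.4 analyses only participants with glucose data from both arms.

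**The concern.** The effect used for sizing comes from one population and the trial enrols a wider one. Both inputs in section 11.3 come from patients with T2DM, and no effect is assumed for prediabetes or for the mixture. The protocol's own account of the pilot places the whole effect in the diabetic patients.

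The primary analysis returns one effect averaged over whatever mix is recruited. Diabetes status is fixed within a person, so in complete pairs its main effect cancels from the treatment contrast. It cannot show whether the effect differs by status.

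If prediabetic participants respond less, the averaged effect falls below 17.2 mg/dl by an amount that depends on an uncontrolled recruitment share. A null average could then be read as no effect of CPAP withdrawal, including in T2DM, where the cited evidence points to one.

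**Working it through.** **Inputs.** Two-sided alpha 0.05, power 0.80 (written as a beta of 0.8), target 17.2 and spread 19.0 mg/dl, 22 completers (section 11.3). Subgroup n=7 with CI 0.13 to 34.6, and whole sample n=31 with mean 5.57 and CI 0.59 to 10.55 (section 5).

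**Method.** Paired t-test with n=22 and 21 df. Noncentrality = effect × √22 / SD of the paired difference; power from the noncentral t distribution. Using 20 df instead changes power by less than half a percentage point.

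**Step 1: reproduce N=22.**
- With 19.0 as a within-patient SD, the paired SD is 19.0 × √2 = 26.9. The noncentrality is 17.2 × 4.69 / 26.9 = 3.0 and power is 82%; 21 participants give just under 80%. So N=22 reproduces. The same convention gives N=18 for 13.5 and 13.5, which also matches.
- With 19.0 as the SD of the paired difference, only 12 participants are needed for 17.2 mg/dl.

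The arithmetic is sound under the first convention.

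**Step 2: which SD does the pilot support?** The subgroup CI has half-width (34.6 − 0.13)/2 = 17.2. Divided by t(0.975, 6 df) = 2.447 this gives an SE of 7.04, and × √7 gives a paired SD of 18.6. That is close to 19.0, so 19.0 looks like a paired-difference SD, although N=22 treats it as within-patient. Both are carried forward.

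**Step 3: smallest effect detectable with 80% power at n=22.** About 16.8 mg/dl at SD 26.9 and 11.9 mg/dl at SD 19.0.

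**Step 4: an effect outside T2DM.** From the pilot, (31 × 5.57 − 7 × 17.2)/24 = (172.7 − 120.4)/24 = 2.2 mg/dl in the 24 non-diabetic patients. This is a stand-in for prediabetes, not a measurement of it. As a milder assumption I take half the T2DM effect, 8.6 mg/dl.

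**Step 5: power with 22 completers.** Averaged effect = share × 17.2 + (1 − share) × prediabetes effect. The T2DM share is not given in the protocol, so the shares below are assumptions.

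| T2DM share | Prediabetes effect | Averaged effect | Power, SD 26.9 | Power, SD 19.0 |
|---|---|---|---|---|
| 100% | n/a | 17.2 | 82% | 98% |
| 75% | 2.2 | 13.4 | 61% | 89% |
| 50% | 2.2 | 9.7 | 36% | 63% |
| 50% | 8.6 | 12.9 | 57% | 86% |

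With 2.2 mg/dl in prediabetes, the T2DM share needed for 80% power is (11.9 − 2.2)/(17.2 − 2.2) = about 65% at SD 19.0, and (16.8 − 2.2)/(17.2 − 2.2) = about 97% at SD 26.9.

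**The case against.** The strongest reply is that section 11.3 makes a conditional statement: 22 participants are enough not to miss 17.2 mg/dl. It does not predict 17.2 mg/dl in the mixed sample, and the number reproduces. Section 5 openly gives the 7 of 31, the lack of pre-planning and the 5.57 mg/dl. The description of the source as T2DM patients fits the patients behind the 17.2. All of this stands, and it makes the issue one of justification rather than of calculation. The second calculation also means that N does not hang on seven patients alone. But it too comes from T2DM patients, so it does not address the mix.

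The SD point also stands. If 19.0 is a paired SD, 22 completers carry real slack, and a mostly T2DM sample would keep more than 80% power.

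The 2.2 mg/dl proxy is pessimistic. Section 5 says that the source did not assess prediabetes, so its 24 non-diabetic patients may include people with normal glucose, whom this trial excludes. Section 5 also cites benefits of CPAP in prediabetes, on insulin sensitivity and glucose tolerance rather than overnight glucose, and suggests that three nights of withdrawal may be too short, against seven here. For the same reason the pilot's overall 5.57 mg/dl should not be carried over as the expected effect: it describes a sample in which 24 of 31 were non-diabetic.

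Finally, group-specific estimates may already be planned in the separate SAP announced in section 11.1. Their absence from section 11.2 is not a fault in itself. An SAP would not, however, correct the sample-size rationale in section 11.3.

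**Conclusion.** The concern holds in a conditional form. The stated 80% power applies if the averaged effect is 17.2 mg/dl. The protocol gives no basis for expecting that in a mixed sample, and its own background suggests a smaller effect outside T2DM. Across the assumptions above, power at a 50:50 mix runs from 36% to 86%, depending on which SD 19.0 is and how prediabetic participants respond.

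A reader might infer that the trial lacks 80% power, or that 80% is reached only in an all-T2DM sample. The documents support neither. At a paired SD of 19.0, about 65% T2DM is enough even with the pessimistic 2.2 mg/dl, and the recruitment share is unknown. What is established is that power for the enrolled population is unstated and depends on a mix that the design does not control. This is a should-fix.

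**What to change.** In section 11.3:
- State that 17.2 mg/dl is a post hoc estimate from 7 diabetic patients, and give the whole-sample 5.57 mg/dl beside it.
- State whether 19.0 is the SD of the paired difference or the within-patient SD.
- Replace the single power claim with power, or the detectable difference, for the mixed sample by T2DM share (for example 50%, 75% and 100%) and by assumed prediabetes effect. The 80% detectable difference at 22 completers is about 11.9 mg/dl at a paired SD of 19.0 and 16.8 mg/dl at 26.9.

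In section 11.2, keep the averaged effect as primary. Add a pre-specified supportive treatment-by-diabetes-status term, and report the withdrawal effect with its 95% CI in T2DM and in prediabetes. A null average is then not read as no effect in T2DM.

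The cost is wording and one supportive model term. The stated power will look less favourable, and the group estimates will be imprecise with 22 completers. No extra patients are needed.

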These studies suggest that treating OSA with CPAP can improve aspects of glycaemic control (74, 75) but they have their limitations. First, Chopra *et al.* (74), only studied patients after 3 nights of CPAP withdrawal, which may be an insufficient period of time for OSA to effect of glycaemic control. In addition, it only included seven diabetic patients and made no assessment of whether other patients were prediabetic. Second, Pamidi *et al.* (75), only looked at morning glucose levels following glucose tolerance tests and did not explore the overnight period that is of most interest. A separate uncontrolled trial has shown that 7 days of CPAP therapy supervised for 8 hours/ night showed a 13.5±13.5 mg/dl improvement in 24 hour blood glucose levels (76). All of these studies are removed from normal clinical care in admitting patients to hospital for between 3 and 14 nights. In addition, these studies included a heterogeneous group of patients with T2DM, "prediabetes" or no diabetes. There is a therefore a need to understand the effects of CPAP on glycaemic control outside of the setting of hospital with careful description of diabetes/prediabetes. In this study we aim to use CPAP withdrawal to assess the effects of OSA on 24-hour glycaemic control over a period of one week in patients with known OSA and diabetes/prediabetes.

Patient involvement in shaping this research

This research has been directly informed from recognising the priorities of patients. We surveyed patients with OSA from the membership of the Sleep Apnoea Trust Association, a patient led OSA support group. We received 585 responses to our survey of their membership. 566 (97%) of the respondents agreed that "research to help understand if OSA causes of worsens diabetes is important". 377 (64%) of respondents would be likely to "consider stopping CPAP for 10-14 days for a research study to enable better understanding of the effects of OSA" (See *Figure 2*).

[figure not shown]

Figure 2: A) Results of response to the statement "research to help understand if OSA causes or worsens diabetes is important. B) Results of response to the question "how likely would it be that you would consider stopping CPAP for 10-14 days for a research study to enable better understanding of the effects of OSA".

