11.7. The Level of Statistical Significance

Statistical significance is defined as a two-sided alpha of 0.05 for this trial.

11.8. Procedure for Accounting for Missing, Unused, and Spurious Data.

Data will not be imputed in the analyses of the primary outcome will be analysed on a completed cases/per-protocol basis.

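### Section 11.3: the 22 participants follow only if the 19.0 mg/dl spread is a single-measurement SD, but the pilot confidence interval points to an SD of the paired difference; the error is conservative

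*Protocol*

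**What the plan says.** Protocol section 11.3 bases the calculation on the difference in mean overnight glucose and gives the reason: "This was chosen as the primary outcome as paired pilot data exists for this outcome". The pilot result is reported as "They found a between group difference of 17.2 19.0 mg/dl" (a plus-minus sign has evidently been lost when the PDF was read, which is no fault of the plan). The conclusion is that a trial "with a two-sided alpha of 0.05 and a beta of 0.8 would require 22 participants in a crossover study".

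An alternative basis is a study of one week of supervised CPAP, which section 5 says "showed a 13.5±13.5 mg/dl improvement in 24 hour blood glucose levels". From this, section 11.3 derives 18 participants. It adopts the larger figure, 22, raises it to 25 for sensor loss and to 30 for drop-out, and stops recruitment once 22 participants have completed per protocol with sufficient glucose data.

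Section 5 describes the pilot as a randomised crossover and reports CPAP withdrawal "increasing blood glucose levels by 17.2mg/dl in diabetic participants (95% CI 0.13, 34.6, p=0.04", adding that "only 7 of 31 patients were diabetic". Section 11.7 confirms the test level: "Statistical significance is defined as a two-sided alpha of 0.05 for this trial".

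**The concern.** In a crossover, the SD that drives the sample size is that of the within-participant difference. If the pilot paper reports the difference with its own SD, that SD goes straight into the paired formula. If the only SD available is the within-participant SD of one measurement, the SD of the difference is √2 times larger and the required number roughly doubles. Section 11.3 does not say which kind of SD it has. Its wording attaches 19.0 to the difference, yet the resulting 22 fits the other reading.

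The 22 matters because it fixes the recruitment stop and underlies the 25 and the 30. If the SD was misread, the stated combination of 80% power and 17.2 mg/dl does not describe the design, and nearly twice the number needed for that stated target would undergo CPAP withdrawal without the margin being declared or justified.

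**Working it through.** **Inputs.** Two-sided alpha 0.05 (11.7). Power 0.80, reading the stated beta of 0.8 as power (11.3). Difference 17.2 and spread 19.0; alternative 13.5 and 13.5 (11.3, section 5). Pilot interval 0.13 to 34.6, p = 0.04, n = 7 (section 5).

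**Method.** Paired t-test with the noncentral t distribution and noncentrality δ√n / SDdiff. The degrees of freedom are n−1, or n−2 with a period term. The normal approximation is n = (1.960 + 0.842)² (SDdiff/δ)² = 7.849 (SDdiff/δ)².

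**1. Reproducing the plan's figures.** Treat each spread as a single-measurement SD, so SDdiff = SD × √2.

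- 19.0 × √2 = 26.87. Normal approximation: 7.849 × (26.87/17.2)² = 19.2. With the t distribution, n = 21 gives 79.7% and n = 22 gives 81.7% (81.5% with a period term). Result: **22**, as stated.
- 13.5 × √2 = 19.09. Normal approximation: 15.7. With the t distribution, n = 17 gives 78.1% and n = 18 gives 80.7% (80.4% with a period term). Result: **18**, as stated.

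**2. Treating the spreads as SDs of the paired difference.**

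- 17.2 and 19.0: normal approximation 7.849 × (19.0/17.2)² = 9.6. With the t distribution, n = 11 gives 77.2% and n = 12 gives 81.4%. Result: **12**, with or without a period term.
- 13.5 and 13.5: normal approximation 7.8. Result with the t distribution: **10**, or **11** with a period term.
- A higher power does not explain the stated pair. 90% would give 15 to 16 and 13; 95% would give 18 to 19 and 16.

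**3. Which reading of 19.0 fits the protocol's own interval?** The half-width is (34.6 − 0.13)/2 = 17.235.

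- t-based (6 df): 17.235/2.447 = 7.04, and 7.04 × √7 = **18.6**.
- z-based: 17.235/1.96 = 8.79, and 8.79 × √7 = **23.3**.
- From p = 0.04 with 6 df: **17.4**.

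In the other direction, SDdiff 19.0 with n = 7 implies an interval of −0.4 to 34.8 (t-based), close to the reported one. SDdiff 26.9 implies −7.7 to 42.1 (t-based, p = 0.14) or −2.7 to 37.1 (z-based, p = 0.09). Neither agrees with a reported interval that excludes zero.

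**4. What 22 completers deliver.**

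| SDdiff (mg/dl) | n for 80% power at 17.2 | Power at n = 22 for 17.2 | Difference with 80% power at n = 22 |
|---|---|---|---|
| 19.0 | 12 | 98% | 11.9 |
| 23.3 | 17 | 91% | 14.6 |
| 26.9 | 22 | 82% | 16.8 |

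**The case against.** Four points can be made for leaving the section alone.

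- **The error is on the safe side.** The section promises that 17.2 mg/dl will not be missed, and 22 completers meet that promise on every SD in the table. This stands and limits the severity.
- **The cross-check on 19.0 is not decisive.** The protocol does not say how the pilot interval was computed, and the figures do not cohere fully. The midpoint is 17.365 rather than 17.2, and the back-solved standard errors give p of about 0.050 rather than 0.04. This is why the result is given as a range. No reading tried reaches 26.9.
- **The SD is itself poorly known.** It comes from 7 patients in an unplanned subgroup. Assuming normal differences, the 95% chi-square interval for an SD of 19.0 on 6 df is about 12.2 to 41.8, so the difference detectable at n = 22 could lie anywhere from about 7.7 to 26.2 mg/dl. The pilot used venous sampling, whereas this trial uses home glucose sensors (mean absolute relative difference 10–12%, section 5) and also admits prediabetes. A larger planning SD could well be prudent. That stands as a reason to inflate, but section 11.3 claims no such allowance and presents 22 as following from the pilot figures.
- **A null result would be read mainly from the observed confidence interval,** which uses the trial's own variance. This is right, so the planning error should not be said to distort the eventual inference.

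A reader might also infer that both spreads are proven to be SDs of the difference. For 13.5 the documents give no sample size, interval or p-value. That reading rests only on its attachment to an improvement, and 18 is not the number adopted.

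**Conclusion.** The stated 22 does not follow from the stated inputs when 19.0 is read as section 11.3 words it and as the section 5 interval supports. The paired calculation gives 12, or 17 if the pilot interval was z-based. One identifiable step, an unstated factor of √2 on the SD, reproduces both 22 and 18 exactly. On the paired reading, 22 completers have about 91% to 98% power for 17.2 mg/dl, and 80% power for about 11.9 to 14.6 mg/dl.

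This rests on a paired t analysis, on 80% power being intended, and on the pilot interval being a simple t or z interval for 7 paired differences. For 13.5, the reading as an SD of the difference is an assumption.

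Two stronger inferences are not supported. The trial is not underpowered for its stated target, because the error runs the other way. Nor does a beta of 0.8 mean that the trial was planned with 20% power: the figures reproduce at 80% power, so it is a slip of wording. The point is a moderate one about a wrongly stated design property, not a reason to change the number enrolled.

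**What to change.** In section 11.3:

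1. State for 19.0 and for 13.5 whether each is an SD of the paired difference or of a single measurement, after checking the two source papers.
2. If 19.0 is an SD of the difference, do one of the following:
   - keep 22 completers and restate what they provide: 80% power for about 11.9 to 14.6 mg/dl for an SD of the difference of 19.0 to 23.3, noting that this SD comes from 7 patients; or
   - declare 26.9 as the planning SD of the difference and give the reason, for example home sensor readings in place of venous sampling. This keeps 22 for 17.2 mg/dl.
3. Replace the beta of 0.8, in both places, by power of 0.8 (beta 0.2).

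The cost is a few sentences in one section. The recruitment stop, the number randomised and the analysis stay as they are.

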A Cochrane review showed that the use of CGM can improve HbA_{1c} levels in patients with type 1 diabetes mellitus (T1DM) but leads to increased hypoglycaemia when used to direct insulin pump therapy, compared to standard glucose monitoring (48). This has led to NICE recommending their use for a limited number of patients with T1DM, including those with hypoglycaemic difficulties and those with an elevated HbA_{1c} despite frequent monitoring (49). CGM does have drawbacks, particularly with accuracy of their recordings. CGMs do not measure blood or plasma glucose levels, instead they measure interstitial fluid glucose levels. Whilst interstitial glucose levels are closely related to blood and plasma glucose levels they are probably less accurate than standard blood glucose monitoring and gold-standard laboratory glucose measurements, with mean absolute relative differences of between 10-12% for both "flash" and "true" CGM devices (50-53). The differences in measurement however, have little impact on clinical outcome with 85-87% of results leading to the same clinical management and 99% of results leading to the same clinical outcome with CGM, compared to standard glucose monitoring (50, 51). There is a lag-time of 4.5 ± 4.8 minutes for changes in blood glucose levels to be reflected in changes in interstitial CGM readings. Despite, CGM being slightly less accurate than blood glucose monitoring the ability to continuously monitor glucose levels overnight without admission to hospital means this is an ideal way to monitor the effects of OSA on glycaemic control. In addition, 98.6% of patients found the pain of CGM as acceptable or better than standard glucose monitoring (50). The device we intend to use - the Dexcom G6 - has a 10 day sensor life, with 87% of monitors surviving to 10 days (53).

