9.6.1. Description of study procedure(s)

Bloods

Participants will have blood samples taken at the screening visits and visits 1, 2, 3 and 4. These will be performed using sterile technique using standard venepuncture technique. Samples will be analysed as detailed below.

Continuous glucose monitoring

At visits 1 and 3 participants will have continuous glucose monitoring supplied and established (G6 sensor and transmitter, Dexcom). They consist of a sensor with of a small needle, usually the width of a small hair attached to a patch that is inserted under the skin on the upper arm or the abdomen. The researcher will fit the participant with the sensor using a one-touch applicator to insert a small sensor just beneath the skin, either sited on the upper arm or the abdomen (participant's preference). This will be performed as per the manufacturers standard operating procedures. The device will then continuously record glucose levels. This device will then be worn for seven days until it is removed at visit 2. The device is water resistant meaning that participants will be able to shower but not swim or bathe during the trial.

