11.4. Analysis Populations

As this is a physiological mechanistic study, analysis will be on all evaluable participants and not on an intention-to-treat basis. Analysis will be conducted on all evaluable participants defined as participants who have evaluable CGM data from Days 5, 6, and 7 of both treatment arms, and who have completed the trial as per protocol.

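### The sensor-loss allowance in Section 11.3 is applied once although each evaluable participant needs two working sensors, and the synopsis gives 25 where Section 11.3 gives 30

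*Protocol*

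**What the plan says.** Section 11.3 of the protocol sets the base requirement: "would require 22 participants in a crossover study". It then makes two allowances. The first is for sensor loss: "allowing for only 87% of CGM monitoring sensors surviving the 10 day follow-up period (53) from application, gives 25 patients". The second is a 10% drop-out rate, described as more conservative than the 1% seen in earlier parallel withdrawal trials, after which "we will aim to randomise 30 patients". The same paragraph ends recruitment once 22 participants have completed per protocol with sufficient CGM data.

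Other sections bear on the first allowance:

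- **Two sensors.** The procedures table in Section 9 (note a) and Sections 9.7 and 9.8 have a monitor fitted at Visit 1 and another at Visit 3.
- **Seven days of wear.** Section 9.6.1 says of the first sensor: "This device will then be worn for seven days until it is removed at visit 2". Section 9.8 places Visit 4 seven days after Visit 3. Section 5 makes clear that the 87% is survival to 10 days.
- **Both periods required.** Section 11.4 defines evaluable participants by "evaluable CGM data from Days 5, 6, and 7 of both treatment arms" and per-protocol completion. Section 11.8 rules out imputation for the primary outcome.
- **Replacement.** Section 9.10 says that withdrawals and discontinuations are replaced.

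The synopsis (Section 3) gives the sample size as 25.

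**The concern.** The 87% is a rate per sensor, but the plan uses it as if it were a rate per participant. A sensor failure in either period removes the participant from the primary analysis, because data from both arms are needed and nothing is imputed. The loss therefore applies twice.

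Separately, the protocol carries two sample sizes. The synopsis figure of 25 is neither the evaluable target (22) nor the number to randomise (30). It matches the intermediate step in Section 11.3, before drop-out is allowed for, and the synopsis does not label it as such.

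At stake is whether the planned number to randomise can be expected to deliver the 22 on which the power statement rests, and whether approvals, registration and reports quote the same target.

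**Working it through.** **Inputs.** From Section 11.3: 22 evaluable; difference 17.2 mg/dl with 19.0 taken as its SD; two-sided alpha 0.05; power 0.80 (written there as a beta of 0.8); sensor survival 0.87; drop-out 10% (1% in earlier trials). From Sections 9 and 11.4: two sensors per participant, both needed.

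**Step 1: the plan's base figure.** For a two-period crossover t-test with N − 2 degrees of freedom and standard error 19.0 × √(2/N), with 19.0 as the within-patient SD, power is 0.795 at N = 21 and 0.815 at N = 22. The 22 is reproduced.

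**Step 2: the plan's inflation.** 22/0.87 = 25.3, stated as 25 (26 if rounded up). 25.3/0.9 = 28.1 and 26/0.9 = 28.9; the plan randomises 30, slightly more. With one sensor per participant, 30 would yield 30 × 0.87 × 0.9 = 23.5 on average, with an 81% chance of at least 22.

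**Step 3: two sensors.** Assuming independent failures, both survive with probability 0.87² = 0.757.

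- Before drop-out: 22/0.757 = 29.1.
- With 10% drop-out: 22/(0.87² × 0.9) = 32.3, so 33.
- Yield from 30: 30 × 0.87² × 0.9 = 20.4.

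**Step 4: sensitivity.** Let s be survival per sensor and d the drop-out rate. The probability that a randomised participant is evaluable is p = s² × (1 − d); the chance of at least 22 is the binomial tail. The 0.907 is 0.87^0.7, which converts the 10-day figure to 7 days under an assumed constant failure hazard. The 0.95 is an illustrative assumption.

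| s | d | 22/p | Mean evaluable from 30 | Chance of ≥22 from 30 | Mean evaluable from 25 | Chance of ≥22 from 25 |
|---|---|---|---|---|---|---|
| 0.87 | 10% | 32.3 | 20.4 | 35% | 17.0 | 2% |
| 0.87 | 1% | 29.4 | 22.5 | 67% | 18.7 | 10% |
| 0.907 | 10% | 29.7 | 22.2 | 63% | 18.5 | 8% |
| 0.907 | 1% | 27.0 | 24.4 | 91% | 20.4 | 29% |
| 0.95 | 10% | 27.1 | 24.4 | 91% | 20.3 | 28% |

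With 30 randomised and 10% drop-out, the break-even survival for an expected 22 is √(22/27) = 0.903 per sensor.

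**Step 5: effect on power if the number fell short.** On the reading that reproduces 22, power is 0.81 at 22 evaluable and 0.77 at 20.

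**The case against.** The strongest reply is that the protocol ties recruitment to the outcome that matters. Thirty is worded as an aim, recruitment ends only when 22 have completed with sufficient CGM data, and withdrawals are replaced. A reader might infer from the 35% and 2% chances that the trial will end short of 22 and be underpowered. The documents do not support that: those chances apply only if 30 or 25 is a fixed limit, and no section says that either is. What remains is that the aim itself is derived wrongly, and that Section 9.10 replaces withdrawals and discontinuations, which does not clearly cover a participant who completes the trial but loses a sensor.

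A second reply is that 87% and 10% are both pessimistic here. This largely stands. The 87% covers 10 days against 7 days of wear, and earlier drop-out was 1%. With either input relaxed, 30 is about right, as the table shows. Failures that cluster within a participant would also reduce the loss below the independent figure. The protocol makes none of these arguments, so 30 is adequate, if it is, through errors that happen to offset each other.

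A third reply is that even 20 evaluable costs little power (0.77 against 0.81). It costs less still if 19.0 is the SD of the paired difference: a paired t-test with 20 then has power 0.97. The interval in Section 5 for seven diabetic patients (0.13 to 34.6) points that way, since it implies an SD of the difference of about 18.6. This too stands, and it limits the consequence.

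A reader might also count it as an error that 25/0.9 = 27.8 is not 30. It is not one: the plan never equates the two, and rounding up is cautious.

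**Conclusion.** The point holds as an error in the stated sample size. Section 11.3 counts one sensor where its own evaluability rule needs two. On its own 87% and 10%, with independent failures, the number to randomise is 33 rather than 30, and 30 gives 20.4 evaluable on average. The gap is small and depends on the inputs: it closes if 7-day survival is about 0.90 or better, or if drop-out is near 1%. The conflict between 25 in the synopsis and 30 in Section 11.3 does not depend on any survival assumption, and 25 gives a low chance of 22 evaluable in every row of the table.

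Because recruitment continues to 22 per-protocol completers with sufficient data, the error falls on the planned number to randomise. It would reach the power of the final analysis only if 25 or 30 were treated as a cap.

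**What to change.** 1. Give one number to randomise, the same in the synopsis and Section 11.3, and label 22 as the evaluable target.
2. Derive it as 22/(s² × 0.9), with s the survival of one sensor over 7 days of wear, and state the source of s or the assumption behind it. Show the result over a range: 33 at s = 0.87, 30 at 0.907 and 28 at 0.95, each with the expected number evaluable.
3. If 30 is kept, state its expected yield and say that it is an estimate, with recruitment continuing to 22 evaluable participants. Say that completers lost to sensor failure are replaced as well as withdrawals. Do not call 30 a ceiling: that would conflict with replacement in Section 9.10 and would create the shortfall that the allowance is meant to prevent.

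The cost is protocol wording. If 30 is kept as the estimate, the planned number does not rise.
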